3.9.2 Clinical Laboratory Evaluation

A list of clinical laboratory tests is given in Table 3.

Table 3. List of Laboratory Tests

Hematology	
 - Hematocrit - Hemoglobin - Mean corpuscular hemoglobin - Mean corpuscular hemoglobin concentration (MCHC) 	
 - Mean corpuscular volume - Platelet count - Red blood cell (RBC) count - White blood cell (WBC) count with differential
Serum Chemistry and Electrolytes	
 - Albumin - Alanine aminotransferase (ALT) - Aspartate aminotransferase (AST) - Blood urea nitrogen (BUN) - Glucose - Bicarbonate (HCO₃) - Creatinine Chloride (Cl) - Total protein 	
 - Calcium (Ca) - Magnesium - Phosphorus - Potassium (K) - Sodium (Na) - Total bilirubin - Direct bilirubin - Uric acid
Glycemic Control	
 - Fasting plasma glucose (FPG) - Hemoglobin A1c (HbA1c) 	
Serum Lipids	
 - Total cholesterol (TC) - High-density lipoprotein cholesterol (HDL-C) - Triglycerides (TG) 	
 - Low-density lipoprotein cholesterol (LDL-C), calculated - LDL-C, direct5
Urinalysis¹	
 - Appearance - Bilirubin 	
 - Nitrite - Occult blood

	
 - Color - Glucose - Ketones 	
 - pH - Protein - Specific gravity - Urobilinogen - Leukocyte esterase
Urine Drug Screen¹	
 - Amphetamines - Barbiturates - Cocaine Metabolites 	
 - Opiates - Benzodiazepines - Cannabinoids
Infectious Disease Testing¹	
 - HBsAg 	
 - HCV

¹ Urinalysis, urine drug screen parameters and infectious disease testing parameters will be listed only.

Continuous laboratory data will be examined for trends using descriptive statistics of changes from baseline to each planned post-baseline visit. These data will also be categorized as low, normal or high based on the reference ranges of the central laboratory. The number and percentage of subjects with indicated shifts relative to the laboratory normal ranges (low, normal, high) in their results from baseline to each post-baseline visit will be presented by category for all applicable laboratory parameters listed in Table 3. The analyses will be performed using the safety analysis set and presented by treatment group.

A separate listing for all clinically significant laboratory abnormalities will be provided.

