1. Missing HbA1c data (for weeks 2, 6, or 12) will be imputed via multiple imputation, following which the MMRM will be repeated on the complete datasets with results combined across complete datasets using standard MI techniques; HbA1c values collected after the start of rescue medication will be considered missing.
2. Missing HbA1c data will be imputed via LOCF, following which the MMRM will be repeated; HbA1c values collected after the start of rescue medication will be considered missing.
3. HbA1c values collected after the start of rescue medication will NOT be considered missing, and the MMRM analyses will be re-performed.

The effect of bexagliflozin on fasting blood glucose, blood pressure, body weight, change in HbA1c over time, and proportion of subjects who reach HbA1c < 7% will be evaluated as secondary endpoints. These endpoints are considered exploratory and will not be adjusted for multiplicity.

Safety and tolerability of bexagliflozin in subjects with T2DM will also be assessed descriptively. Data summaries will be produced for AEs, physical exam results, vital signs, ECG results, and clinical lab results including serum chemistry, hematology, serum lipids, glycemic control parameters and urinalysis.

Date of Original Approved Protocol: 29 September 2014

Date of Revised Protocol: 16 February 2015

LIST OF ABBREVIATIONS AND DEFINITIONS OF TERMS

ADA	American Diabetic Association
AE	Adverse event
ALT	Alanine aminotransferase
ALP	Alkaline phosphatase
ANCOVA	Analysis of covariance
ANOVA	Analysis of variance
AST	Aspartate aminotransferase
ATC	Anatomic therapeutic chemical
BMI	Body mass index
BUN	Blood urea nitrogen
CI	Confidence interval
CK	Creatinine kinase
CRF	Case report form
CRO	Contract research organization
CV	Cardiovascular
DPP4	Dipeptidyl peptidase 4
DSMB	Data and Safety Monitoring Board
ECG	Electrocardiogram
eGFR	Estimated glomerular filtration rate
FAS	Full analysis set
FPG	Fasting plasma glucose
γ -GTP	Gamma-glutamyl transferase
GCP	Good Clinical Practice
GLP-1	Glucagon-like peptide-1
h	Hour
HbA1c	Glycated hemoglobin
HBsAg	Hepatitis B surface antigen
Hct	Hematocrit
HCV	Hepatitis C virus
HDPE	High density polyethylene
HF	Heart failure
Hgb	Hemoglobin
HIPAA	Health Information Portability and Accountability Act
HIV	Human immunodeficiency virus
ICCR	In country caretaker representative
ICH	International Conference on Harmonisation
IEC	Independent Ethics Committee
IND	Investigational New Drug

IRAE	Immediately reportable adverse event

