9.6 Analysis of Safety

All safety analyses will be conducted based on the Safety Analysis Set.

Safety data will include AEs, physical exam results, vital signs, ECG results, and clinical lab measurements of serum chemistry, hematology, serum lipids, glycemic control parameters and urine specimens. Observed data will be listed by subject and summarized using descriptive statistics by treatment group based on the Safety Analysis Set.

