9.6.1 Adverse Events

Adverse events will be mapped to preferred term and body system using the Medical Dictionary for Regulatory Activities (MedDRA). AEs that begin after the first administration of investigational products or existing AEs that worsen after the first dose of study medication are considered treatment emergent AEs (TEAEs). TEAEs will be assigned to the run-in period or the double blind randomization period in the same manner. The number and percentage of subjects reporting TEAEs will be summarized for each treatment group by MedDRA system organ class and preferred term, then by severity, and by relationship to study treatment. Drug-related AEs will be considered those to be at least possibly related to

investigational product based on the investigator's assessment. The number and percentage of subjects reporting serious AEs, and the number and percentage of subjects reporting AEs leading to treatment discontinuation will also be summarized for each treatment group by MedDRA system organ class and preferred term

Adverse event listings will be provided for the following subsets:

1. All TEAEs
2. All TEAEs at least possibly related to bexagliflozin
3. Serious AEs (if any)
4. AEs leading to treatment discontinuation (if any)

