9.6.4 Physical Examination

Physical examination findings including body weight will be collected at baseline and during the treatment period, safety extension phase and at follow-up. Abnormal findings at each visit will be tabulated as incidences by body system.

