3.9.1.5 Deaths, Serious AEs and AEs That Led to Discontinuation

Subject data listings of fatal AEs, serious AEs, AEs that led to treatment discontinuation and AEs that led to study withdrawal will be presented.

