3.9.5 Physical Examination and Body Weight

Physical exam findings and body weight will be included in a subject listing.

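### The SAP reduces to listings four by-arm safety tables that the protocol commits to: urinalysis, serious AEs by term, AEs leading to discontinuation by term, and abnormal examination findings

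*SAP*

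**What the plan says.** **Protocol.** Section 9.6 names physical examination results among the safety data, and its laboratory measurements extend to "glycemic control parameters and urine specimens". It then says: "Observed data will be listed by subject and summarized using descriptive statistics by treatment group based on the Safety Analysis Set". A listing and a summary are therefore both required. The synopsis agrees: the data summaries it promises include physical examination results and "clinical lab results including serum chemistry, hematology, serum lipids, glycemic control parameters and urinalysis". Section 9.6.3 adds shift tables of laboratory abnormalities for each treatment. Section 9.6.1 promises the number and percentage of subjects with serious AEs, and says that "subjects reporting AEs leading to treatment discontinuation will also be summarized for each treatment group by MedDRA system organ class and preferred term". Section 9.6.4 says of the physical examination: "Abnormal findings at each visit will be tabulated as incidences by body system".

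**SAP.** Footnote 1 to Table 3 in Section 3.9.2 reads: "Urinalysis, urine drug screen parameters and infectious disease testing parameters will be listed only". Section 3.9.1.5 reads, in full: "Subject data listings of fatal AEs, serious AEs, AEs that led to treatment discontinuation and AEs that led to study withdrawal will be presented". Section 3.9.5 reads: "Physical exam findings and body weight will be included in a subject listing". The SAP introduction says that its methods are based on Section 9 of protocol Version 2, dated 16 February 2015. That is the revision date of the protocol under review, so a difference in versions does not explain the mismatch.

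**The concern.** This is a dose-range-finding trial, and assessing safety is one of its stated objectives. Urinary tract infection, acid-base disorders and renal failure events are pre-specified events of special interest. Urinalysis at V2, V3, V4 and V5 yields ketones, protein, blood, leukocyte esterase and nitrite, all of which bear on those events. A listing holds the values but does not compare the doses. SAP Section 4 also orders listings, by default, by subject number within study center, so the four arms are interleaved.

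For serious AEs and AEs leading to discontinuation, a total per arm shows whether the arms differ. It does not show which kind of event drives a difference, and the protocol promised that breakdown. A SAP that departs from its protocol should say so. A reader of the study report would otherwise expect tables that were never planned.

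**Working it through.** No figure in the plan needs to be reproduced. The check sets each protocol commitment against the SAP text and the SAP's index of tables and listings.

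| Protocol commitment | SAP rule | SAP table | SAP listing |
|---|---|---|---|
| Urine results summarized by arm (synopsis, 9.6); laboratory shift tables (9.6.3) | Listed only (3.9.2, Table 3 footnote 1) | none | 16.2.8.3 |
| Serious AEs by arm, SOC and PT (9.6.1) | Listing (3.9.1.5) | none | 16.2.7.2 |
| AEs leading to treatment discontinuation by arm, SOC and PT (9.6.1) | Listing (3.9.1.5) | none | 16.2.7.3 |
| Abnormal examination findings by body system and visit (9.6.4), by arm (9.6) | Listing (3.9.5) | none | 16.2.12 |

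**Index check.** SAP Section 5.1 has 12 safety tables: 14.3.1.1 to 14.3.1.4 (4), 14.3.2 and 14.3.3 (2), 14.3.4.1.1, 14.3.4.1.2, 14.3.4.2.1 and 14.3.4.2.2 (4), and 14.3.5 and 14.3.6 (2); 4 + 2 + 4 + 2 = 12. Their titles cover overall AEs, AEs by term, by severity and by relatedness, special-interest events, hypoglycemia, hematology, chemistry with glycemic control and lipids, vital signs, and ECG. None covers any row above. The laboratory shift text in 3.9.2 refers to the applicable parameters of Table 3, and the footnote takes urinalysis out of that set.

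**What remains by arm.**
- Section 3.9.1.1 and Table 14.3.1.1 give subjects with at least one serious TEAE, related serious TEAE, TEAE leading to drug discontinuation, TEAE leading to study withdrawal, or fatal TEAE.
- Sections 3.9.1.2 and 3.9.1.4 give all TEAEs and related TEAEs by SOC and PT.
- Section 3.9.1.6 and Table 14.3.2 give each special-interest category by SOC and PT, including urinary tract infection, genital mycotic infection, acid-base disorders and renal failure events.
- Section 3.9.2 gives serum bicarbonate, creatinine and BUN as changes and shifts (Tables 14.3.4.2.1 and 14.3.4.2.2).
- Body weight, which protocol 9.6.4 groups with the examination, is summarized and modeled as an efficacy endpoint (Tables 14.2.5.1 to 14.2.5.3).

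**What is lost.** Subtracting the second list from the protocol's commitments leaves two things. One is the SOC/PT breakdown of serious events and of discontinuation events. The other is any comparison across doses of urinalysis results and examination findings that no investigator reported as an AE.

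**What the footnote does not lose.** Urine drug screen and infectious disease tests are done at screening only (protocol Table 1 and Appendix 2). Listing them removes no post-baseline comparison. Only the urinalysis part of the footnote conflicts with the protocol.

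**The case against.** The strongest reply is that the safety comparison is largely intact. An overall excess of serious events or discontinuations in one arm would show in Table 14.3.1.1. Infection, acid-base and renal events are compared directly in Table 14.3.2. Laboratory changes that the investigator judges clinically significant are AEs by definition (protocol 6.10), so they reach the TEAE tables. With about 80 subjects per arm treated for 12 weeks, serious events may be few enough to count from a listing, although the documents give no expected rate.

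Most of this stands. A reader might infer from the missing tables that imbalances between arms could not be seen at all. The documents do not support that, for the reasons just given. Nor does the volume of urinalysis results in Listing 16.2.8.3 measure the harm, since a row count says nothing about what a by-arm table would detect.

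A reader might also count the absence of a urine-culture table as a further departure. It is not one. Cultures are conditional on symptoms or a positive site dipstick (protocol 6.10.6), and no part of protocol Section 9 promises a table of them. Such a table is optional.

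The reply does not remove the contradiction. The special-interest tables count reported events. A dose-related shift in ketones, protein, blood, leukocyte esterase or nitrite that no one reports as an AE reaches no by-arm table, and the same holds for examination findings.

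**Conclusion.** The point holds as a reporting conflict of moderate weight. Four committed sets of by-arm tables have no counterpart among the SAP's 12 safety tables, and the SAP text available gives no reason. The primary analysis and the main adverse-event comparisons are untouched. The gap is fullest for urinalysis and examination findings, which have no by-arm table of any kind. It is partial for serious and discontinuation events, where the totals survive and the breakdown does not.

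Two assumptions carry this. The first is that the list in SAP Section 5.1 is complete, which agrees with the text of Section 3.9. The second is that the by-arm requirement in protocol 9.6 governs the examination table in 9.6.4, whose own sentence does not mention treatment group.

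**What to change.** Before unblinding, amend SAP Sections 3.9 and 5.1.

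- Take urinalysis out of footnote 1 to Table 3. Leave the drug screen and infectious disease tests there.
- Add a by-arm table of urinalysis shifts from baseline by visit, for at least ketones, protein, blood, leukocyte esterase and nitrite. Define the result categories, because the low/normal/high scheme does not suit every urinalysis parameter.
- Add serious TEAEs by arm, SOC and PT.
- Add TEAEs leading to treatment discontinuation by arm, SOC and PT.
- Add abnormal examination findings by arm, body system and visit. The complete examinations at S1 and V5 and the abbreviated ones at S5 and V4 differ in scope, so the table should state which body systems were examined at each visit.

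If the sponsor means to keep any of the four as a listing, the SAP should state the departure from protocol 9.6 and justify it. The cost is a few standard tables from data already collected, with no change to study conduct.

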6.10 Adverse Events Assessments

Adverse event (AE): Any untoward medical occurrence experienced by a subject administered an investigational product. An AE does not necessarily have a causal relationship with treatment. An AE can therefore be any unfavorable and unintended accident, sign (including an abnormal laboratory finding), symptom, or disease occurring during the period of use of an investigational product or the period of follow-up, whether or not related to the investigational product.

Serious adverse event (SAE): Any event that results in any of the following outcomes:

1. Death
2. A life-threatening event, *i.e.*, the subject was, in the opinion of the investigator, at immediate risk of death from the event as it occurred (this does not include an event that, had it occurred in a more severe form, might have caused death)
3. A persistent or significant disability/incapacity
4. An event that requires hospitalization or prolongs hospitalization
5. A congenital anomaly/birth defect
6. Any other medically significant events that, based upon appropriate medical judgment, may harm the subject and may require medical or surgical intervention to prevent one of the outcomes listed above, *e.g.* allergic bronchospasm requiring intensive treatment in an emergency room or home; blood dyscrasias or convulsions that do not result in hospitalization; or the development of drug dependency or drug abuse.

Non-serious adverse events are all events that do not meet the criteria for a serious adverse event.

Immediately Reportable Adverse Event (IRAE): Any serious adverse event or any adverse event that necessitates discontinuation of investigational product, including pregnancy.

Clinical Laboratory Changes: It is the investigator's responsibility to review the results of all laboratory tests as they become available. For each abnormal laboratory test result the investigator needs to ascertain if this is a clinically significant change from baseline for that individual subject (this determination, however, does not necessarily need to be made the first time an abnormal value is observed. The investigator may repeat the laboratory test or request additional tests to verify the results of the original laboratory tests). If the laboratory

value is determined to be a clinically significant and abnormal change from baseline for that subject, this is considered an AE.

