3.1.9 Analysis Visit Windows

Visit windows for study conduct are specified in footnote 1 of Table 1: Schedule of Events. Treatment period visits are planned for Day 1, Randomization (V1: Week 0),

Day 15 (V2: Week 2), Day 43 (V3: Week 6) and Day 85 (V4: Week 12). There is also a scheduled follow-up visit at Day 99 (V5: Week 14). A visit window of ± 3 days is allowed for all visits except for Week 0. Week 0 (Study Day 1, Randomization) is to be scheduled at 3 days after the last run-in visit (Visit S5) and can be extended to 5 days pending on HbA1c value availability.

For any unscheduled visits, Table 2 will be used to map the unscheduled assessments to the analysis visits prior to selection of records for analysis

Table 2: Nominal (Targeted) Time Points and Analysis Visit Windows

Assessment	Nominal (Targeted) Time Point	Analysis Visit Window (Interval in Study Days)
Baseline Assessments	Week 0 (Study Day 1)	\leq Day 1
Post-Baseline Assessments	Week 2 (Study Day 15)	Day 8 through Day 22
	Week 6 (Study Day 43)	Day 36 through Day 50
	Week 12 (Study Day 85)	Day 78 through Day 92
	Week 14 (Study Day 99)	Day 93 through Day 105

After mapping the data to the analysis visits, the following rules will apply unless otherwise specified for a particular analysis:

- If multiple records are available within a single analysis visit window, the record closest to the planned assessment day will be selected for analysis.
- If 2 records are equidistant from the target day, then the first record will be selected.
- If a subject has no record in an analysis window, the subject will be considered missing at that time point.

For subjects withdrawing early, the end of study data (early termination visit) will be mapped according to the analysis visit windows in Table 2 for summarization and analysis. However, if the visit does not fall within any of the analysis visit windows then the visit will be mapped to the next scheduled time point.

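### The by-visit laboratory tables keep one record per window and can leave out abnormal unscheduled or superseded results, and no table counts subjects by arm by their worst post-baseline value

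*SAP*

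**What the plan says.** SAP 3.9.2 plans two laboratory summaries: descriptive statistics of change to each planned visit, and low/normal/high shifts in which subjects' changes "in their results from baseline to each post-baseline visit will be presented by category for all applicable laboratory parameters listed in Table 3". The table list in SAP 5.1 (Tables 14.3.4.1.1 to 14.3.4.2.2) contains nothing else for laboratory data, and in particular no worst or any-time post-baseline category.

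The choice of record comes from SAP 3.1.9. "For any unscheduled visits, Table 2 will be used to map the unscheduled assessments to the analysis visits", and then "If multiple records are available within a single analysis visit window, the record closest to the planned assessment day will be selected for analysis". For ties, "If 2 records are equidistant from the target day, then the first record will be selected". These are defaults: "the following rules will apply unless otherwise specified for a particular analysis". SAP 3.9.2 specifies nothing different.

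Protocol 6.10 allows for repeat tests after an abnormal result: "The investigator may repeat the laboratory test or request additional tests to verify the results of the original laboratory" tests. Protocol 6.10.8 fixes an interval in one case: ALT or AST above 3 x ULN is repeated within 48 to 72 h.

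**The concern.** Keeping the record nearest the target day makes sense for an efficacy profile, where one representative value per visit is wanted. For laboratory safety the extreme value is usually of more interest, and this rule ignores it. An abnormal Week 2 result on Day 12 followed by a normal repeat on Day 15 is tabulated as normal. An abnormal unscheduled result on Day 20 after a normal Day 15 visit is not tabulated. An abnormal result on, say, Day 30 belongs to no window.

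Elsewhere the SAP does count the worst occurrence per subject: adverse events at maximum severity (3.9.1.3) and hypoglycemia at the most severe category (3.9.1.7). Laboratory data are treated differently, and no reason is given.

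What is at stake is the comparison between arms of how many subjects went out of range at any time on treatment. This matters most for analytes without a numeric trigger for an adverse event, such as creatinine, bicarbonate, potassium and hemoglobin.

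**Working it through.** The plan states no figure on this point, so there is none to reproduce. The check applies the stated rules to study days.

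**Inputs**
- Windows (SAP Table 2): Week 2, target Day 15, "Day 8 through Day 22"; Week 6, target Day 43, "Day 36 through Day 50"; Week 12, target Day 85, Days 78 to 92; Week 14, target Day 99, Days 93 to 105.
- Scheduled visits may fall within ±3 days of target (SAP 3.1.9).
- Post-baseline hematology and chemistry are drawn at V2, V4 and V5, not at V3 (SAP 2.2.4; Protocol Appendix 2).
- About 80 subjects per arm (SAP 2.2.1).

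**1. Days that belong to no window**
- Days 2 to 85 are 84 on-treatment days after Day 1.
- The gaps are Days 2–7 (6 days), 23–35 (13) and 51–77 (27): 6 + 13 + 27 = 46, and 46/84 = 55%.
- If Week 6 is not tabulated for chemistry and hematology because nothing is scheduled then, its 15 days are lost as well: 46 + 15 = 61, and 61/84 = 73%.
- One exception: early-termination data outside every window are moved to the next scheduled time point.

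**2. When a repeat replaces the scheduled result**
- Let the visit fall k days before target and the repeat r days after the visit. The repeat is selected if |r − k| < k, that is if 0 < r < 2k. A tie goes to the earlier record. If the visit is on or after target, a later repeat is never nearer.
- With r = 2 or 3 (48 to 72 h): k = 3 gives 2k = 6, so the repeat is selected; k = 2 gives 2k = 4, selected; k = 1 gives 2k = 2, not selected.
- The repeat therefore wins on Days 12–13, 82–83 and 96–97, which is 2 of the 7 allowed days at each of Weeks 2, 12 and 14. On the other 5 days the scheduled result is kept.
- The protocol sets the 48 to 72 h interval only for ALT/AST, so for other analytes r is an assumption. With r = 1 the repeat wins on 3 of 7 days (k = 1, 2, 3). With r = 4 or 5 it wins on 1 of 7 (k = 3). With r of 6 or more it wins on none.

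**3. By-visit against ever-abnormal (illustration only)**
This is a separate matter from the nearest-record rule. The gap below would exist even with no repeats and no unscheduled draws. It shows only what a missing any-time category can hide.
- Assume a 4% chance of an abnormal value per draw; the documents give no figure.
- At each visit: 0.04 × 80 = 3.2, about 3 of 80.
- There are two scheduled on-treatment draws, Weeks 2 and 12. If the abnormality is fully persistent, ever-abnormal is 4%. If the draws are independent, it is 1 − 0.96² = 7.8%, and 0.078 × 80 = 6.3, about 6 of 80.

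**The case against.** A reader might infer that abnormal unscheduled results vanish from the report. They do not. All laboratory data are listed (Listings 16.2.8.1 and 16.2.8.2), and clinically significant abnormalities have their own listing (16.2.8.4). Unscheduled results are also used when they are the only or the nearest record in a window, so an abnormal repeat can equally replace a normal result.

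There is also a route by arm through adverse events. Protocol 6.10 makes any clinically significant abnormal change an adverse event, and likewise any AST, ALT or bilirubin above 3 x ULN. These are tabulated by arm (SAP 3.9.1.2). Hepatotoxicity, acid-base disorders and renal failure events are events of special interest, summarized by arm without regard to visit windows (SAP 3.9.1.6). This stands, and it narrows the point to out-of-range values not recorded as adverse events. It does not remove it: outside liver tests and low glucose the route depends on the investigator's judgement, which Protocol 6.10 allows to wait for a repeat. A normal repeat may then both replace the tabulated value and lead to no adverse event.

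A reader might also infer that the monitoring committee cannot see such events. It does receive the adverse event listing (16.2.7.1). For values that are not adverse events, however, its only laboratory source is Tables 14.3.4.x, restricted to ALT, AST, creatinine, bicarbonate and hemoglobin. The laboratory listings are not marked for it.

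Finally, one might count three draws and conclude that incidence is understated nearly threefold (1 − 0.96³ = 11.5% against 4%). That counts Week 14, two weeks after the last dose. A by-visit percentage is also a different quantity rather than an understated one.

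Protocol 9.6.3 asks only for changes from baseline, shift tables and listed abnormalities, which the SAP delivers, and the rule is the same in every arm.

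**Conclusion.** The point holds in limited form. The by-visit laboratory tables can omit abnormal unscheduled or superseded results, and no table counts subjects by arm by worst post-baseline value.

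In size, a normal repeat displaces an abnormal scheduled result on 2 of 7 allowed visit days, assuming a 48 to 72 h repeat. Results on 46 of 84 on-treatment days (61 of 84 if Week 6 is not tabulated for these tests) generally feed no by-visit table. How many subjects this affects cannot be derived, because the documents give no rate of unscheduled testing or of abnormality; the 4% to 7.8% range is illustrative.

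The documents do not support calling the data lost or the planned tables incorrect. What is missing is a by-arm summary of out-of-range values that never became adverse events. Adding it is an inexpensive improvement to a descriptive safety analysis and leaves the efficacy results untouched.

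**What to change.** In SAP 3.9.2, add to Tables 14.3.4.1.2 and 14.3.4.2.2 a shift from baseline to worst on-treatment value, with lowest and highest shown separately. Use every scheduled and unscheduled central-laboratory result after the first dose up to an on-treatment cut-off that the SAP states, and show V5 follow-up separately so that off-drug values are not mixed in.

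State that the nearest-record rule still governs by-visit means and by-visit shifts, which need a rule for choosing among several records, but not the worst-value rows. Say also whether Week 6 is tabulated for chemistry and hematology. Both tables already go to the monitoring committee, so the new rows would reach it for the five parameters it receives.

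The cost is additional rows for each laboratory parameter and the programming for them. No new data are needed.
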